Number of Patients	Approximately 1000 patients will be recruited from approximately 100 sites in the US and Canada.
Study Procedures	Details of the physician's practice setting will be recorded once for each site; treatment logistics will be recorded at the first treatment session for each patient.  Patients considering treatment for improvement of SM fullness due to SMF will be recruited. Eligible patients will be enrolled in the registry and data will be collected from patients who elect treatment until their SMF reduction treatment is completed or discontinued. Patients who do not initially elect treatment will be followed to determine whether or not they subsequently undergo treatment, and if not, until up to one year has elapsed since enrollment and no treatment has been elected. Physicians will treat and assess patients according to their discretion.  At enrollment, data on previous relevant SMF and facial aesthetic treatment(s) will be collected from the patients, and as necessary, their medical records, along with baseline SMF assessments and information on treatment goals. Demography (birth date, sex, race, ethnic origin), Clinical Information (height, weight, lifestyle habits), and a brief medical history (including diabetes, cardiovascular disease) will be collected, Information including treatment received for SMF reduction, treatment procedures and outcomes, follow-up assessments of SMF, and adverse events (AEs) will be recorded at subsequent clinic visits or telephone contacts (Data for Collection). Patient medical history data will be updated, as appropriate, at the first treatment visit.
Data Collection Procedures	Electronic data capture (EDC) will be used for participating sites to record clinical data, data questionnaires and assessment data via electronic case report forms (eCRFs) accessed through a secure internet portal. Data entry screens will be designed to efficiently capture the desired data elements from patient medical records (Data for Collection).
Data Elements	Physician Practice Profile At each site, the physician will complete the Physician Practice Setting Questionnaire, including the following information:  • Physician characteristics:  - Clinical history / specialty, including board certification  - Years of aesthetic practice  - Percent of practice focused on facial aesthetics  - Physician approach to discussing new treatment options  - Number and roles of physicians and other healthcare providers (HCPs) in the

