Statistical Methods	A formal statistical analysis plan (SAP) that will provide details of all analyses and presentation of registry data will be approved prior to data analysis.
	Descriptive statistics will comprise the number of observations (n), mean, standard deviation (SD), median, minimum, and maximum for continuous variables; and n and percent for categorical variables, with the number of patients who do not have missing values as the denominator.
	No imputation for missing data will be performed. Analyses will be conducted using observed cases.
Sample Size	Up to 1,000 patients are anticipated. The number and size of analysis groups will be determined by the treatments selected by the patients in this sample; therefore, group sizes may not be identical. In general, if the sample size in a treatment cohort is at least 250, this study is well-powered to observe an improvement of at least one grade in the CR-SMFRS (Section 8.1)
Analysis Populations	Analyses will be based upon all patients who were enrolled and have at least one post-baseline visit. Additional subgroups also may be examined, as deemed appropriate (eg, sex, initial assessment scores, prior treatments received).
Practice, Patient, and Treatment Data	Data will be summarized, by type of SMF reduction treatment, with descriptive statistics, and presented in listings.
Outcome Data	SMF Assessments
	Results for SMF assessments will be summarized with descriptive statistics at each time point. Changes from baseline will be summarized descriptively for each

CONFIDENTIAL

gistry Study Protocol

treatment cohort at each post-baseline assessment. Exploratory analysis of covariance (ANCOVA) methods will also be used to assess change from baseline at the end-of-treatment follow-up timepoint, where treatment type and baseline score will be included in the model. The ANCOVA results will be generated in SAS using PROC MIXED. Cochran-Mantel-Haenszel (CMH) tests for association, stratified by site, will be used to assess categorical responses. The qualification for a "responder" for each SMF assessment will be further defined in the SAP. For the CR-SMFRS and PR-SMFRS assessments, the number and percent of patients in each treatment cohort who have at least a 1-grade improvement will be presented, along with the corresponding 95% confidence interval (CI). Responses to the other SMF assessments will be summarized similarly.

Protocol ATX-101-15-40M

Amendment 2: 20 Oct 2015

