#### 3 STUDY CONDUCT

# 3.1 Design of the Study

This is a prospective, non-interventional, longitudinal, multi-center registry to be conducted in patients with SM fullness due to SMF. Each participating physician will prescribe treatments based on his or her usual clinical practice, and no restriction on the use of commercially available treatments will be imposed. As this is a non-interventional study, the patient-physician relationship will not be affected, nor will there be any influence on the therapeutic management of the patient.

Study visits, procedures, and evaluations are summarized in Data for Collection and described in detail in Sections 5 and 6.

Patients considering treatment to reduce SMF will be recruited. Eligible patients will be enrolled in the registry, and patients who elect treatment will be followed until their SMF reduction treatment is completed or discontinued. Patients who do not initially elect treatment will be followed to determine whether or not they subsequently undergo treatmentuntil up to one year has elapsed since enrollment and no treatment has been elected. Reasons for treatment discontinuation, or for the decision to not receive treatment, will be recorded. Enrolled patients will be assessed regularly by their treating physician according to usual clinical practice. Data collection is anticipated to continue for approximately 15 months. The duration of individual patient participation will vary depending on the chosen treatment method and individual requirements.

At Enrollment, relevant data on previous SMF and facial aesthetic treatments will be collected from the patients, and as necessary, from their medical records. Additionally, baseline assessments of SMF will be performed. Details of the investigator's practice setting will be recorded after site initiation, and details of treatment logistics will be recorded at the first treatment session(s) (for each treatment selected) for patients who elect treatment for SMF reduction . Information, including treatment received for SMF reduction, treatment procedures and outcomes, follow-up assessments of SMF, and adverse events (AEs) will be recorded at subsequent clinic visits or telephone contacts. Patient medical history data will be updated, as appropriate, at the first treatment session (Baseline Treatment Visit).

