# 8.1 Sample Size

Up to 1000 patients are anticipated. No pre-specified statistical hypotheses will be tested, therefore no formal power calculations were performed. Instead, the precision of 95% confidence intervals around key response variables was estimated. Note that the number and size of analysis groups will be determined by the treatments selected by the patients in this sample; therefore, group sizes may not be identical.

Table 1 below provides 2-sided 95% confidence interval (CI) around an expected response rate of 67.5% for CR-SMFRS score in patients treated with ATX-101 during Phase 3 clinical trials, where response was defined as an improvement of at least one grade.

Table 1 Precision and 95% Confidence Intervals for Various Sample Sizes, Based on an Expected Patient Response Rate of 67.5%

Sample size (N) 250	95% CI 61.7, 73.3	500	63.4, 71.6
750	64.1, 70.9		

Table 2 below provides the 2-sided 95% CI around expected levels of patient satisfaction rates. 13

Table 2 Precision and 95% Confidence Intervals for Various Combinations of Sample Size and Patient Satisfaction Rates

	Probable Rates of Patient-reported Satisfaction				
_	80%	85%	90%		
Sample Size (N)	95% CI	95% CI	95% CI		
250	75.0, 85.0	80.6, 89.4	86.3, 93.7		
500	76.5, 83.5	81.9, 88.1	87.4, 92.6		
750	77.1, 82.9	82.4, 87.6	87.9, 92.1		

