# 8.2.2.1 Main Efficacy Endpoint: Submental Fat (SMF) Assessments

The following SMF assessments (Appendix 11) are planned at each visit:

- Clinician-Reported Submental Fat Rating Scale (CR-SMFRS) score
- Patient-Reported Submental Fat Rating Scale (PR-SMFRS) score
- Patient-Reported Submental Fat Impact Scale (PR-SMFIS) score
- Submental Skin Laxity Grade (SMSLG)
- Subject Self Rating Scale (SSRS)
- Patient Self-Perception of Age (SPA) scale
- Patient Global Questions

Overall and individual component summaries for each scale, where applicable, will be provided using descriptive statistics at each timepoint. Changes from baseline will be summarized descriptively for each treatment cohort at each post-baseline assessment. Exploratory analysis of covariance (ANCOVA) methods will also be used to assess change from baseline at the end-of-treatment follow-up timepoint, where treatment type and baseline score will be included in the model. The ANCOVA results will be generated in SAS using PROC MIXED. Cochran-Mantel-Haenszel (CMH) tests for association, stratified by site, will be used to assess the responses.

For CR-SMFRS and PR-SMFRS assessments, the number and percent of patients in each treatment cohort who are responders, ie, have at least a 1-grade improvement, will be presented, along with the corresponding 95% CI. Responses to the other SMF assessments will be summarized similarly.

For the SSRS, a subject is defined as a responder for the assessment if the response was positive relative to the score's neutral response option (ie, "slightly satisfied," "somewhat satisfied," or "extremely satisfied" where neutral is "neither satisfied nor dissatisfied").

An SMSLG responder at an assessment time is defined as a subject who stayed the same SMSLG score or had improvement in SMSLG score relative to baseline. This scale is different from the others in that "no change" is counted as a responder. The reason for this distinction is

that the intent is not to investigate whether ATX-101 reduces/improves skin laxity, but rather to investigate whether ATX-101 is associated with an undesirable increase in skin laxity. Accordingly, the categories are, effectively, skin laxity either "did not increase" or "did increase."

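### The responder tests adjust for site but omit the baseline score that the ANCOVA on the same scale includes, although treatment is chosen rather than randomised

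*Protocol*

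**What the plan says.** Section 8.2.2.1 names two inferential methods for the submental fat scales.

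- **Change from baseline:** an exploratory ANCOVA at end of treatment, "where treatment type and baseline score will be included in the model". Site is not mentioned.
- **Responses:** "Cochran-Mantel-Haenszel (CMH) tests for association, stratified by site, will be used to assess the responses". The synopsis (Outcome Data) says the same: "Cochran-Mantel-Haenszel (CMH) tests for association, stratified by site, will be used to assess categorical responses". Baseline is not mentioned.

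For CR-SMFRS and PR-SMFRS, the number and percent of patients "who are responders, ie, have at least a 1-grade improvement, will be presented, along with the corresponding 95% CI".

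The baseline value is available. Section 3.1 says of the Enrollment visit: "Additionally, baseline assessments of SMF will be performed".

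Treatment is not allocated by the study: "Each participating physician will prescribe treatments based on his or her usual clinical practice" (Section 3.1). Section 8.1 adds that "the number and size of analysis groups will be determined by the treatments selected by the patients in this sample". On size, the synopsis states: "Approximately 1000 patients will be recruited from approximately 100 sites in the US and Canada".

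Section 9.8.2 intends to adjust for predictors of treatment selection and outcome where applicable. Section 9.8.3 expects patient characteristics to be linked to both.

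**The concern.** On one scale, the mean-change analysis adjusts for baseline but not site, and the response analysis adjusts for site but not baseline. No reason is given.

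The starting grade matters for a responder defined by a 1-grade drop. On the 0 to 4 CR-SMFRS, a patient at grade 1 can respond only by reaching 0, while a patient at grade 3 has three grades to fall. Section 4.1 sets no minimum grade. Defining response as change from baseline does not adjust for baseline; it is what creates this floor.

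Physician and patient choose treatment knowing the severity, so grade is a plausible confounder, and site strata do not remove it. The responder test could then show a treatment difference that reflects only starting severity, or mask a real one. It could also disagree with the ANCOVA merely because one adjusts for baseline and the other does not. Separately, with small sites, strata holding only one treatment drop out of the test.

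**Working it through.** **1. The plan's own figure.** Table 1 in Section 8.1 reproduces as a Wald interval: 0.675 ± 1.96 × √(0.675 × 0.325 / 250) = 0.675 ± 0.058, that is 61.7 to 73.3%. The rows for 500 and 750 also match. These figures concern precision within a cohort. The protocol gives no figure for the CMH test, so every input in steps 3 to 5 is an assumption unless a section is named.

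**2. Single-treatment sites.** For a site with N patients, n1 on one of two treatments, m1 responders, and a responders on that treatment, the CMH contributions are:

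- numerator: a − n1·m1/N
- variance: n1(N − n1)·m1(N − m1) / [N²(N − 1)]

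If n1 = N, then a = m1 and both are zero. If n1 = 0, both are zero. Every such site contributes nothing.

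About 1000 patients over about 100 sites (synopsis) is about 10 enrolled per site; treated patients will be fewer. If all sites share a dominant-treatment share q, the chance that a 10-patient site has one treatment only is q^10 + (1 − q)^10:

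| q | 0.5 | 0.7 | 0.8 | 0.9 | 0.95 |
|---|---|---|---|---|---|
| single-treatment sites | 0.2% | 2.8% | 10.7% | 34.9% | 59.9% |

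With a 70:30 mix and site-specific preference (beta-binomial, between-site correlation ρ), the share is 9% at ρ = 0.1, 45% at 0.5 and 88% at 0.9. The protocol gives neither q nor ρ.

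**3. False positives when grade mix differs.** Assumptions:

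- 100 sites of 10 patients, two treatments at 75:25, no treatment effect, no site effect
- response of 30, 65, 75 and 80% at grades 1 to 4
- grade mix 20/45/28/7% on one treatment and 8/32/42/18% on the other

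Response rates produced by grade mix alone:

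- 0.20×0.30 + 0.45×0.65 + 0.28×0.75 + 0.07×0.80 = 61.9%
- 0.08×0.30 + 0.32×0.65 + 0.42×0.75 + 0.18×0.80 = 69.1%

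The spurious difference is 7.25 points. With the milder mix on the larger group, the pooled rate is 0.75×0.6185 + 0.25×0.691 = 0.637 and the standard error is √(0.637 × 0.363 × (1/750 + 1/250)) = 0.0351. So z = 0.0725/0.0351 = 2.06 before stratifying.

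Within-site comparison keeps about 0.9(1 − ρ) of the information, so z becomes 2.06 × √[0.9(1 − ρ)] and the rejection rate is about Φ(z − 1.96):

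| Site preference | ρ | Informative sites of 100 | z | Rejects, by formula | Rejects, simulated (2000 runs) |
|---|---|---|---|---|---|
| none | 0 | 94 | 1.96 | 50% | 48–53% |
| moderate | 1/3 | 65 | 1.60 | 36% | 33–37% |
| strong | 2/3 | 34 | 1.13 | 20% | 20–22% |

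With baseline grade in the strata, the simulated rate is about 5%. With equal grade mix, the site-only test also holds about 5%.

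**4. A second design.** Here the mix is 70:30 with two grade levels, responding at 60% vs 75% or at 55% vs 80%. Site-only CMH rejects in 11 to 29% of null runs for a 20-point difference in the share at the higher grade, and in 22 to 81% for a 40-point difference. Site × grade strata give 4 to 6%. With no grade difference, the site-only test gives 4 to 6%.

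**5. Whether grade could replace site.** Add a site effect of SD 1.0 on the logit scale, strong site preference, equal grade mix and no treatment effect. Grade-only strata then reject in about 15 to 18% of runs, while site-only strata stay at 4 to 5%. Site × grade strata hold about 5 to 6%. Their cost is power: 29 to 70%, against 35 to 76% for site-only strata, at a log odds ratio of 0.5 with equal mix and no site effect.

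**The case against.** The strongest defence is one of weight. Sections 8.1 and 8.2.2 state no formal hypotheses and call the inferential tests exploratory. The specified responder output is a count, percent and 95% CI per cohort, where patients from single-treatment sites count in full. Section 9.8.2 intends adjustment where applicable, Section 8.2.1 mentions initial assessment scores as a possible grouping, and the SAP, not shown here, may add a model. All of this lowers the stakes. It does not cure the text, because the protocol does name the test and its stratum.

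It also stands that the inflation needs both a grade gradient and an imbalance, and the protocol quantifies neither. The extreme floor case, a patient at grade 0, is close to moot for CR-SMFRS because inclusion criterion 1 requires fullness due to submental fat.

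Three stronger readings are tempting but unsupported:

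- **That most sites will drop out.** The single-treatment share runs from under 1% to about 90% depending on the assumption, and the protocol gives no treatment mix by site.
- **That moving to grade strata would recover much power.** A simulation with no site effect shows 85% power for grade strata against 35 to 77% for site strata. Part of that gap is between-site information, which site stratification is meant to exclude. It is not efficiency wrongly lost.
- **That grade should replace site.** CR-SMFRS is scored by each site's own clinician and Section 9.8.2 expects provider characteristics to matter, so site effects are plausible. Step 5 of the working shows the resulting error.

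**Conclusion.** The point holds in a limited form. The responder test is fixed with site as its only stratum and leaves out a collected baseline score that the companion ANCOVA uses, in a study where treatment is chosen. If grade mix differs between treatments, the test can mistake starting severity for a treatment effect. The size is about 20 to 50% rejection at nominal 5% under the assumed rates and imbalance in step 3, and about 5% if the mix is balanced. The first range illustrates the problem and is not a forecast.

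Single-treatment sites contribute exactly zero; how many there will be is unknown. Site adjustment itself is reasonable and should stay. Because the tests are exploratory, this is a change worth making but not a critical flaw.

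**What to change.** In Section 8.2.2.1, the synopsis and the SAP, for responder tests of scales that have an Enrollment score:

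- Use logistic regression on treatment type and baseline score while retaining site, for example as a random intercept.
- If CMH is preferred, add baseline grade to the site strata; do not substitute it for site.
- Keep the site-stratified CMH as a sensitivity analysis, and report how many sites and patients are informative.

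No new data are needed. The model assumes a distribution for site effects and gives a model-based odds ratio in place of a simple test. Crossing site by grade in CMH costs some power, about 6 points in the simulated settings (70 against 76%, 29 against 35%).

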# 8.2.2.2 Other Efficacy Endpoints: Physician and Patient Questionnaires

The categorical responses observed for the physician and patient questionnaires will be summarized using counts, percents, and 95% CIs for each treatment type.

# 8.2.2.3 Safety Analysis

AEs will be coded using MedDRA Version 18.0 or later. AE and AE mitigation data will be summarized with descriptive statistics, by type of SMF reduction treatment, system organ class (SOC), and preferred term (PT), and presented in listings. The duration (days) and severity of pain, swelling, and bruising will be summarized by type of SMF reduction treatment, by treatment session, and overall. When a patient has an occurrence of a PT more than once, the patient's average duration for the PT will be computed for the overall summary. Pain scores from the Pain Numeric Rating Scale will be summarized with descriptive statistics by type of SMF reduction treatment and time point.

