#### 5.1.4 Final Visit

The patient's Final Visit will take place either at the last scheduled follow-up visit after completion of all SMF reduction treatment(s), within 3 months of the last treatment session (for each treatment selected), when a patient elects to discontinue treatment, or prior to study closure (treated patients). Information on AE/SAEs, treatment outcomes, and End-of Study assessments will be recorded (section 5.3.4). For patients who do not elect treatment for SMF reduction (untreated patients), the reason for not selecting treatment will be captured at this time point.

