# **Adverse Events:**

- Frequency, severity, duration, medication or other treatment required, and outcome of AEs during and after each SMF reduction treatment session
  - At the end-of-treatment visit, patients will have treatment areas examined and be interviewed in an open-ended manner to solicit reports of AEs since the last visit.
  - Patient calls to clinic with post-treatment concerns /symptoms that meet the definition of AEs (eg, pain, swelling, bruising, numbness) will be included in the AE record.

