#### **6.3** Reporting Procedures for All Adverse Events

All AEs observed by the investigator or reported by the patient will be recorded on the appropriate CRF, irrespective of relationship to SMF reduction treatment. Medically significant AEs will be followed until resolved or considered stable. For each event, the investigator will record a description, dates of onset and resolution, severity, and relationship to SMF reduction treatment. The investigator may be required to provide follow-up information.

Any AE that results in withdrawal from the study must be reported to Allergan after the decision to withdraw is made.

Any death occurring during the study must be reported to Allergan within 24 hours of discovery of the event. This includes any death that occurs within 30 days after the patient's final visit, irrespective of when the final visit occurs.

Pregnancy If a female patient becomes pregnant during the study, the investigator will notify Allergan immediately after the pregnancy is confirmed. Pregnancies are reportable to Allergan in the same timeframe as SAEs:

- Upon learning of a pregnancy occurring in a patient, notify Allergan within 24 hours
- Follow pregnancy until the outcome is known and once this known you must report the outcome to Allegan
- Use the Relevant Allergan Pregnancy Reporting Form
- Pre-Pregnancy and Post-Pregnancy information should be collected, as relevant
- Also complete a SAE Form if outcome results in a serious criteria

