# 8 STATISTICAL METHODS

A formal statistical analysis plan (SAP) that will provide details of all analyses and presentation of registry data will be approved prior to database lock and data analysis.

Descriptive statistics will comprise the number of observations (n), mean, standard deviation (SD), median, minimum, and maximum for continuous variables; and n and percent for categorical variables, with the number of patients who do not have missing values as the denominator.

For this registry, no imputation for missing data will be performed. Analyses will be conducted using observed cases.

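### Pain, swelling or bruising still open at last contact has no computable duration under the observed-case rule, so the duration summary would tend to come out too short

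*Protocol*

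**What the plan says.** Section 8.2.2.3 makes duration a named safety summary: "The duration (days) and severity of pain, swelling, and bruising will be summarized by type of SMF reduction treatment, by treatment session, and overall". For a patient with the same preferred term more than once, "the patient's average duration for the PT will be computed for the overall summary". The synopsis repeats both statements.

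Duration rests on dates. Section 6.3: "For each event, the investigator will record a description, dates of onset and resolution, severity, and relationship to SMF reduction treatment". The same section gives one rule on how long events are pursued: "Medically significant AEs will be followed until resolved or considered stable". It gives no such rule for other AEs.

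Section 8 limits continuous summaries to n, mean, SD, median, minimum and maximum, and adds that "no imputation for missing data will be performed. Analyses will be conducted using observed cases". AE dates are not excepted.

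In section 5.1.4, a treated patient's Final Visit falls no later than three months after the last session, or at discontinuation of treatment, or before the study closes. No minimum interval is set. Up to then, at each visit, "patients will have treatment areas examined and be interviewed in an open-ended manner to solicit reports of AEs since the last visit". The outcome of each AE is also recorded (sections 5.3.2 to 5.3.4).

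**The concern.** An event that has not resolved when the patient is last seen has an onset date and no resolution date. Its true duration is known only to exceed the time observed, which makes it right-censored. If the observed-case rule is applied as written, its duration is a missing value and leaves the mean and the median. Events still open at last contact tend to be the long ones, so the loss is selective.

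Section 2 lists the risks of treatment and the safety profile of the treatments among what the registry is to describe. How long pain, swelling and bruising last is a large part of that for a cosmetic procedure. The table is also split by treatment type. Sections 5.1.2 and 5.1.3 say that the number and spacing of sessions vary by treatment, so the loss need not be equal across the columns.

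**Working it through.** The protocol gives no AE duration and no share of unresolved events, so it has no figure of its own to reproduce on this point.

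**Chain of provisions.** Duration needs a resolution date (6.3). Follow-up to resolution or stability is promised only for medically significant AEs (6.3), and an event closed as stable may also lack an end date. Observation can end soon after the last session (5.1.4). Missing values are not imputed, and observed cases are analysed with ordinary descriptive statistics (8). No provision says what duration an open event receives.

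**Size, on assumed inputs.** Let D be the true duration, exponential with mean m = median / ln 2, and let C be the time from onset to last contact, independent of D. An event enters the summary only if D ≤ C.

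- C fixed: share unresolved = exp(-C/m); mean of resolved events = m - C·exp(-C/m) / (1 - exp(-C/m)).
- C uniform on 0 to T, with e = exp(-T/m): share unresolved u = (m/T)(1 - e); mean of resolved events = (A - B/T) / (1 - u), where A = m - (T + m)e and B = 2m² - (T² + 2mT + 2m²)e.

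Example: median 30 days, m = 30/0.6931 = 43.28.
- C = 90: exp(-90/43.28) = 0.125, so 12.5% are unresolved. Resolved mean = 43.28 - 90 × 0.125/0.875 = 30.42 days, a bias of -30%.
- C uniform on 0 to 90: u = (43.28/90) × 0.875 = 0.421; A = 26.62; B = 1291.8; resolved mean = (26.62 - 14.35)/0.579 = 21.2 days, a bias of -51%.

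| True median (days) | True mean | C = 90 days: unresolved; resolved mean (bias) | C uniform 0-90: unresolved; resolved mean (bias) |
|---|---|---|---|
| 3 | 4.33 | 0.0%; 4.33 (0%) | 4.8%; 4.11 (-5%) |
| 7 | 10.10 | 0.01%; 10.09 (-0.1%) | 11.2%; 8.82 (-13%) |
| 14 | 20.20 | 1.2%; 19.14 (-5%) | 22.2%; 14.74 (-27%) |
| 30 | 43.28 | 12.5%; 30.42 (-30%) | 42.1%; 21.18 (-51%) |

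Earlier last contact goes further: with C = 28 days the bias is -19% at a median of 7 days and -46% at 14 days. With lognormal durations (log-SD 1, by simulation) and a median of 7 days, the bias is -6% for C = 90 and -21% for C uniform.

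**Comparison between treatments.** Assume a median of 30 days for both treatments, sessions 30 days apart and a last visit 30 days after the last session. With one session, C = 30, half the events are unresolved, and the resolved mean is 43.28 - 30 × 0.5/0.5 = 13.3 days. With four sessions, C is 120, 90, 60 and 30 days. The resolved shares are 0.9375, 0.875, 0.75 and 0.5, so 23% are unresolved, and the resolved mean is (33.08 + 26.62 + 17.46 + 6.64)/3.0625 = 27.4 days. The same true duration would be tabulated as 13 days in one column and 27 in the other.

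**With censoring.** Kaplan-Meier on simulated exponential data with C uniform on 0 to 90 days gave medians of 7.0, 14.0 and 30.0 days where the true values were 7, 14 and 30. The resolved-only medians were 6.2, 10.7 and 16.5. The Kaplan-Meier median could not be estimated in scenarios where about half or more of the events were still open at a short fixed last contact.

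**The case against.** The strongest reply is that the protocol nowhere says ongoing events are excluded. Section 8 leaves the details of all analyses to an SAP, and a ban on imputation does not ban censoring. Outcome is recorded, so open events can be identified, and they will appear in the listings. It is true that exclusion is inferred. But the protocol itself fixes the observed-case rule and the list of statistics, and names no censored-data method. An SAP that simply follows those rules produces the omission.

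Three stronger readings are tempting, and the document does not support them.

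- A reader might infer that most events are not followed to resolution. The protocol asks for a resolution date for every event, re-examines the treatment area at each visit and adds patient calls to the AE record. Only events open at last contact are affected, and their share is not given.
- A reader might take it as established that reported durations will be materially too short. With durations of a few days and a Final Visit near three months, which section 5.1.4 allows, the bias is negligible.
- A reader might call the per-patient average an error. It stops one patient from counting repeatedly, it applies only to the overall summary, and the by-session table and the maximum remain. It is a defensible choice.

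The difference between treatments is likewise a possibility that follows from varying session numbers and visit timing. The protocol gives nothing from which to measure it.

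**Conclusion.** The point holds as a gap created by provisions of the protocol read together: events open at last contact have no computable duration and, under the stated rules, would be left out. The direction is clear as long as time to last contact is unrelated to how long the event lasts. The size is not known. It is about 0% for medians of 3 to 7 days with last contact at 90 days, and about -50% for a median of 30 days with last contact uniform over 0 to 90 days; a shorter window would make it larger. All of these rest on assumed duration distributions and assumed last-contact times. The change is worth making because it is cheap and because nobody reading the resulting table could tell which case applied.

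**What to change.** In section 8.2.2.3, and in the SAP, add that for pain, swelling and bruising:

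- the number and percent of events ongoing at last contact are reported by treatment type and session;
- time from onset to resolution is summarised by Kaplan-Meier (median and quartiles where estimable), with unresolved events censored at last contact, by treatment type and session.

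This fills in no values, so it is consistent with the rule against imputation, and it uses onset and resolution dates and AE outcome that are already collected. Kaplan-Meier assumes that censoring is unrelated to duration. Some patients may stop treatment because of a persisting symptom, so the count of ongoing events should stand beside the curve estimates.

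The cost is one more table and a sentence or two of text, and reported durations may become somewhat longer. Showing each patient's longest duration beside the average is optional.
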